The BDC is a leading clinical T1DM clinical and research center. All study personnel will attend an investigator's meeting, which will be organized and conducted before trial initiation. All subjects will sign an informed consent form approved by Western Institutional Review Board (WIRB) and the Colorado Multiple Institutional Review Board (COMIRB).

Study results will be presented at national and international conferences including the Scientific Sessions of the American Diabetes Association (ADA), EASD, ATTD, etc. The Principal Investigator may submit study results for publishing to peer reviewed scientific journals, particularly within the fields of diabetes and endocrinology.

Table 1: Study Procedures for Subjects

Visit	1	2	3 - 13	14
Study Week	0	1	5-40	44-52
Informed Consent and Eligibility Criteria	X			
Demographic Data, Medical History	X			
Concomitant Medications	X	X	X	X
Adverse Events	X	X	X	X
Physical Exam	X	X	X*	X
Urine Pregnancy Test		X		
A1C	X	X	X	X
Vital Signs, Height, Weight	X	X	X	X
Record Basal, Bolus, Total Insulin Dose**	X	X	X	X
SMBG Questionnaire		X	X*	X
Glucose Meter Download	X	X	X	X
Insulin Pump Download (if applicable)	X	X	X	X
Dexcom™ CGM Training and Education (if needed, Groups 1 & 2)		X		
CGM sensor insertion		X	X	
CGM Removal/ Download		X	X	X
Record interventions of a 3 rd party for a subject's high or low glucose levels		X	X	X
Hypoglycemic Fear Questionnaire		X	X*	X
BDC Pregnancy CGM Post-Partum Questionnaire				X

* Once per trimester.

[figure not shown]
** From insulin pump download or record of patient's MDI insulin use.

Table 2: Study Procedures for Followers

Visit	1	2	3 - 13	14
Study Week	0	1	5-40	44-52
Informed Consent and Eligibility Criteria	X			
Follower Questionnaire			X*	X

* Once per month.

Figure 1 Study design:

*Visit 1 will apply for women screened at a pre-conception counseling visit. Women screened in the 1st trimester may combine visits 1 and 2.

**Visits 3 through 13 for pregnancy care and study follow-up.

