CGM data will be analyzed for mean blood glucose values, time spent in hyperglycemic (>240, >300mg/dl) and hypoglycemic (<50, <70, <80 mg/dl) ranges and various indices of glycemic variability. Laboratory analysis for A1C will be performed at baseline, monthly thereafter during the pregnancy, and post-partum. Routine blood tests will be performed in all subjects in each trimester (see Table 1).

Primary outcomes will be:

- 1) Glucose variability as measured by glucose excursions from self-monitoring blood glucose (SMBG) data through log books and downloads as well as CGM downloads and various indices [J-index, mean amplitude of glycemic excursion (MAGE), high blood glucose index (HBGI), low blood glucose index (LBGI)] from CGM downloads.
- 2) Changes detected by the hypoglycemia fear questionnaire.

Secondary outcomes will be:

- 1) How CGM alone and CGM with Share™ usage affect A1C compared to no CGM use,
- 2) Progression of diabetes complications (retinopathy, nephropathy),
- 3) Maternal and fetal outcomes (eclampsia/pre-eclampsia, live birth rates, birth weight, neonatal hypoglycemia, and other similar measures).

Introduction:

Among the US population, 29.1 million people (9.3%) have diabetes (1). Pre-existing diabetes has to be managed very carefully throughout pregnancy to optimize maternal and fetal outcomes (2). Among women

with T1DM who are pregnant, the tools that we have to regulate maternal glucose control include multiple daily injections (MDI), continuous subcutaneous insulin infusion therapy (CSII) also known as insulin pump therapy, and for high-risk individuals continuous glucose monitoring (CGM) (2). CGM use in pregnancy has been shown to be safe, to reduce the frequency of severe hypoglycemia, and to improve A1C values (3-6). Sensor-augmented pump therapy with CGM use continuously was shown to lower A1C more than intermittent use in pregnant women with T1DM (7). However, few studies have measured changes in glucose variability that occur with CGM use during pregnancy and no studies have evaluated how tools that allow family and friends (followers) to access glucose trends affect outcomes during pregnancy.

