The goal of this prospective, non-randomized, pilot quality improvement study is to evaluate how CGM usage with and without remote monitoring capabilities affects glucose variability, A1C control, and patient-related outcomes compared to non-CGM use in pregnancy among women with T1DM. This study may lead to further investigations about the role of mobile phones and handheld devices (such as iPod touch) for T1DM self-care in pregnancy.

The Barbara Davis Center (BDC) Adult Clinic follows ~3,000 patients with T1DM. [name], MPH is this study's Principal Investigator and the director of the Pregnancy and Women's Health Clinic at the BDC, which includes an extensive multidisciplinary team (physician's assistant, nurse practitioner, registered nurses, certified diabetes educators, registered dieticians, and a social worker). The BDC Pregnancy and Women's Health Clinic has all the necessary resources to perform such a trial. Moreover, the investigators have extensive experience conducting clinical trials, including trials during pregnancy.

Primary Objectives:

The primary objectives of this pilot study are to improve maternal glucose management, to assess the role of CGM usage either alone or with remote monitoring capabilities (Share™) and changes detected by the hypoglycemia fear questionnaire among women with T1DM associated with pregnancy.

Secondary objectives:

1. Assessment of remote monitoring capabilities of followers (Share™ usage) that lead to interventions for hypoglycemia and hyperglycemia that affect subjects wearing CGM.
2. Reduction in A1C from baseline to 3 months with maintained control at 6 and 9 months.
3. Assess progression or stability of diabetes complications (retinopathy, nephropathy).
4. Assess effects of CGM usage on maternal and fetal health outcomes (eclampsia/pre-eclampsia, live birth rates, birth weight, neonatal hypoglycemia, and other similar measures).

Research Design:

What do we intend to do?

We intend to execute a single-center, prospective, non-randomized, 'open-label,' investigator initiated pilot study evaluating the effect of CGM usage with or without remote monitoring capabilities on women with T1D throughout pregnancy and compare outcomes to women who do not use a CGM during pregnancy. We also intend to ask a main follower for each woman about his/her knowledge of extreme glucose values among subjects and interventions on a subject's behalf. See Figure 1 for study design.

How are we going to do the work?

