All subjects will have routine post-partum clinical care between 4 and 6 weeks post-partum. However, a post-partum visit up to 12 weeks post-partum will be accepted as a final study visit. Data on all subjects for medications, vital signs, height/weight, insulin doses, SMBG values, glucometer downloads, insulin pump downloads (if applicable), and CGM downloads (if applicable) will be collected. All subjects will be asked to

collect a 7-point profile for SMBG measurements (blood glucose measurements before meals, 2 hours after meals, and at bedtime) along with meal insulin dosing for 1 week in the post-partum period (see SMBG Questionnaire). A1C will be measured. Subjects will be asked about updated concomitant drugs and any AEs that may have occurred. Subjects in Groups 1 and 2 may have had a Dexcom G4 Platinum CGM® for personal use prior to study participation and may thereafter still wear the device after labor and delivery. In such cases, CGM downloads will be included in study data. On source documents, we will record how often subjects required an intervention for low or high glucose values within the previous month, and the nature of the interventions. Subjects will be administered a questionnaire inquiring about the labor and delivery process, maternal and fetal complications before and after delivery, baby's anthropometrics at birth (weight and length), baby's current age, breastfeeding, and other measures (see *BDC Pregnancy CGM Post-Partum Questionnaire* for details). If the pregnancy ended early (for example, spontaneous abortion or stillbirth) or resulted in fetal or neonatal death (for example, stillbirth) we will obtain data about these outcomes. Each subject will be given a hypoglycemic fear questionnaire. Followers will be asked to fill out their last *Follower Questionnaire* during the post-partum period.

Control Arm:

As outlined in the proposal, the subjects prospectively enrolled in this arm (Group 3) will receive the same care as in the intervention arms (Groups 1 and 2) with the exception of not having access to the Dexcom G4 Platinum CGM® with or without Share™ technology.

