The primary endpoints are glucose variability and changes detected by hypoglycemic fear survey. We will measure indices of glucose variability (mean glucose \pm SD, % of glucose within/above/below target ranges, J Index, High Blood Glucose Index [HBGI], Low Blood Glucose Index [LBGI], Mean Amplitude of Glycemic Excursions [MAGE], CONGA_n) throughout pregnancy using the SMBG 7-point profiles for one week taken once per trimester. Hypoglycemic fear survey results will be assessed once monthly over the pregnancy. We will compare outcomes within individuals over time and between individuals of the different study arms. We will test whether outcomes differ between women using Dexcom alone and women using Dexcom with Share™ using interaction terms, and will stratify analyses if differences by group are greater than 10 mg/dL in mean glucose levels are detected. Since SMBG logs will be taken at multiple time points over the pregnancy and since CGMs will be worn continuously for the duration of each pregnancy, linear mixed models will be used to assess changes in outcome measures (GV, time spent in target below or above target) over time in each trimester of pregnancy. We will use linear mixed models to assess changes in the hypoglycemic fear survey in each month of the pregnancy. Secondary endpoints include A1C differences among study arms. Improvement in glycemic variability parameters with a possible reduction of A1C by 0.3%, measured as the difference of the mean A1C laboratory values of the arms of the study between baseline (0-3 months, first trimester), second trimester (3-6 months), and third trimester (6 to 9 months). Mixed models account for missing data, allow for an unstructured covariance matrix for repeated measures, and account for inter-subjects correlation of measurements. Secondary outcomes will be used

in the same mixed models. Differences in frequency of low alert glucose rates, high alert glucose rates, and interventions for low or high glucose values among the followers for each study arm will be analyzed with student t-tests. A p-value < 0.05 will be considered significant, and we will perform statistical analyses with SAS software (version 9.3, SAS Institute, Cary NC).

Publication Strategy:

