Appendix F

BDC Pregnancy CGM Post-Partum Questionnaire

Subject ID: _____

Clinic Visit: (dd/mmm/yyyy) : _____ / _____ / _____

Post-Partum Week: ___4 to 6 weeks ___6 to 8 weeks ___8 to 10 weeks ___10 to 12 weeks

Pregnancy Outcome Date _____
(dd/mmm/yyyy)

Gestational Age _____ Birth Weight _____ Birth Length _____

Child is still living? Yes No Baby's Sex Male Female

Preterm labor during pregnancy? Yes No

If yes, please describe, including dates of hospital admissions: _____

Delivery type:

Vaginal If yes: Spontaneous Induced Breech Vacuum Forceps

VBAC If yes: Spontaneous Induced

Cesarean Section If yes: Low Transverse Low Vertical Classical Unspecified

Pregnancy complications? Yes No

If yes, check all that apply:

 Placenta previa	 Placenta accreta	 Incompetent cervix
 Hyperemesis gravidarum	 Proteinuria	 Hypoglycemic seizure
 Pregnancy-induced hypertension	 Oligohydramnios	 Polyhydramnios
 Pre-eclampsia	 Eclampsia	 Diabetic ketoacidosis
 HELLP syndrome	 Progression of diabetic complications	
 Small for gestational age baby	 Large for gestational age baby	
 Other _____		

Labor complications? Yes No

If yes, check all that apply:

 Fetal intolerance	 Anesthetic complications	 Pre-eclampsia
 Eclampsia	 Dysfunctional labor	 Seizures during labor
 Cephalopelvic disproportion	 Placental abruption	 Placenta previa
 Shoulder dystocia	 Breech delivery	 Nuchal cord
 Excessive bleeding	 Failure to progress in first stage	
 Failure to progress in second stage	 Other _____	

Neonatal complications? Yes No

If yes, check all that apply:

 Birth trauma/injury	 Hypoglycemia	 Asphyxia

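### Birth weight is a secondary outcome with no scale, gestational-age or sex standardisation, direction of benefit or fitting model, so a difference between arms would mix fetal growth with timing of delivery.

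*Combined protocol and SAP*

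**What the plan says.** The secondary outcomes in the study summary include "Maternal and fetal outcomes (eclampsia/pre-eclampsia, live birth rates, birth weight, neonatal hypoglycemia, and other similar measures". The fourth secondary objective is to "Assess effects of CGM usage on maternal and fetal health outcomes" and repeats the same list. Neither place gives birth weight a unit, a standardisation or a direction in which a change would count as improvement.

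The Statistical Analysis Plan describes linear mixed models for glucose variability by trimester and for the hypoglycemia fear survey by month, and then A1C by trimester. It adds that "Secondary outcomes will be used" in those same models. It names no covariate and does not mention gestational age at delivery, infant sex, a percentile, a z-score or a growth reference.

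Under Visit 14, subjects are administered a post-partum questionnaire that covers "baby's anthropometrics at birth (weight and length". The form (Appendix F) has a line for "Gestational Age _____ Birth Weight _____ Birth Length" and an item "Baby's Sex Male Female". Under pregnancy complications it has tick-boxes for "Small for gestational age baby" and "Large for gestational age baby", with no cut-off or reference. No section says these are to be derived from the recorded weight and gestational age.

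The Control Arm section says that women found by retrospective chart review do not complete the questionnaires. Its list of items to abstract does not name birth weight, gestational age at delivery or infant sex.

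**The concern.** Birth weight in grams depends on how fast the fetus grew and on when it was delivered. In diabetic pregnancy both tails matter. A lower mean may reflect less overgrowth or earlier delivery, and a higher mean may reflect later delivery or more overgrowth. The plan does not say which direction is favourable, and a mean in grams cannot settle it.

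Randomisation does not protect the comparison. Arms are formed by willingness to wear a CGM and by device ownership, and Group 3 is topped up with chart-review women, some from before the study began. Delivery timing could differ between such groups for reasons unrelated to CGM.

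The measure that would separate growth from timing is size for gestational age. It is not a named outcome and appears only as undefined tick-boxes. At stake is whether the objective on fetal outcomes can be answered, and whether a birth-weight difference from this pilot would mislead the larger study it is meant to inform. The primary endpoints are not affected.

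**Working it through.** **The plan's own figures.** The plan gives no SD, effect size or power for birth weight, so there is nothing to reproduce for this outcome. Its one relevant calculation, 40 × 0.20 = 8 drop-outs and 32 completers, is correct but does not bear on the point.

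**Fit of the model.** The mixed models are justified by repeated measurements and an unstructured covariance over time. Birth weight gives one value per birth, so there is no within-woman series to model. The plan therefore contains no analysis that fits birth weight, adjusted or unadjusted.

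**Inputs for the illustration.** Group sizes are from the section on subjects per treatment arm: 10 + 20 = 30 CGM women and 10 prospective no-CGM women are anticipated. The 0.05 level is from the Statistical Analysis Plan and is taken as two-sided. Everything else is an assumption, because the documents give no figure:
- weight gain near term, b = 100 to 250 g per week;
- SD of gestational age at delivery, 2 weeks;
- SD of birth weight at fixed gestational age, 450 g;
- difference in mean delivery timing between arms, 1 week.

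**Shift from timing alone.** Shift = b × difference in weeks, so one week gives 100 to 250 g with identical growth for gestation.

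**Variance due to timing.** Raw variance = 450² + (2b)², and the share removed by standardising = (2b)² / raw variance.

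| b (g/week) | (2b)² | Raw variance | Raw SD (g) | Share removed |
|---|---|---|---|---|
| 100 | 40,000 | 242,500 | 492 | 16% |
| 150 | 90,000 | 292,500 | 541 | 31% |
| 200 | 160,000 | 362,500 | 602 | 44% |
| 250 | 250,000 | 452,500 | 673 | 55% |

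**Chance of p < 0.05 with no difference in growth.** For 30 against 10, SE = raw SD × √(1/30 + 1/10) = raw SD × 0.365. With k = shift / SE, the chance is Φ(k − 1.96) + Φ(−k − 1.96).
- b = 100: SE = 180 g, k = 100/180 = 0.56, chance about 9%.
- b = 250: SE = 246 g, k = 250/246 = 1.02, chance about 17%.

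These compare with a nominal 5%. If the raw SD is instead varied freely from 450 to 600 g and b from 100 to 200 g per week, the range is about 7 to 23%.

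**Direction.** Suppose the weight-for-gestation z-score has mean 0 and its SD narrows from 1.5 to 1.0. The share beyond each of the 10th and 90th percentiles (±1.2816) falls from Φ(−1.2816/1.5) = 19.6% to 10.0%. Large and small for gestational age both roughly halve while the mean z-score does not move. A comparison of means can therefore miss a benefit.

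**Who has the data.** Group 3 may hold 10 prospective and up to 30 chart-review women. Up to 30/40 = 75% of it would have no post-partum form and no listed source for any of the three fields.

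**The case against.** The strongest reply is that this is an omission. A reader might infer that the plan prescribes a raw, unadjusted comparison. It does not: birth weight is one item in a list of outcome areas, and the sentence on secondary outcomes follows text about A1C by trimester. That stands. A comparison in grams is only the literal reading of an outcome named without scale or adjustment.

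A reader might also infer that the trial's measure of size for gestation rests on the mother's own judgement. The documents do not support this. Size for gestation is not a named outcome and could enter only through the closing words about similar measures. The form is administered at a clinic visit and does not say who judges size, so the mother may be relaying a clinician's diagnosis. What remains is that the boxes have no definition.

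A third tempting reading is that delivery timing simply confounds the comparison. Timing comes after exposure and may itself respond to glucose control, so it may be partly a mediator. Standardising answers a question about growth for gestation, not about the total effect on weight. This is a reason to report both, not to leave the scale unstated.

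Finally, nothing in the documents shows a one-week difference between arms, and prospective Group 3 is said to receive the same care apart from the device. The outcome is secondary in a pilot with no formal power, and for prospective women the fields will exist whatever the plan says. All of this limits the weight of the point. It does not remove it, because the plan still applies a 0.05 threshold and has no analysis that fits this outcome.

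**Conclusion.** The point holds as a gap in the definition and analysis of one secondary outcome. Birth weight has no scale, standardisation, direction of benefit or suitable model. Taken literally, the plan gives a comparison in grams between non-randomised arms that cannot separate fetal growth from timing of delivery.

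The size is illustrative and rests wholly on assumptions from outside the documents: 100 to 250 g per one-week difference in mean delivery timing, and about 16 to 55% of raw variance attributable to timing if gestational age has an SD of 2 weeks and weight an SD of 450 g at fixed gestational age. No single figure in that range should be quoted as the effect. The change should be made because a better-defined measure is available at small cost. It concerns interpretation of the fetal-growth result only.

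**What to change.** In the secondary outcomes and the Statistical Analysis Plan:
- Define the fetal-growth outcome as birth weight standardised for gestational age and sex (z-score) against one named reference.
- Compare it between arms with a single-measurement model, such as linear regression on arm with stated baseline covariates, in place of the repeated-measures model.
- Derive large and small for gestational age by a stated percentile rule (for example, above the 90th and below the 10th) from the same fields, and use the tick-boxes only as a check.
- Report raw birth weight and gestational age at delivery by arm beside it, because timing may itself be affected by glucose control.

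In the Control Arm section, add birth weight, gestational age at delivery and infant sex to the chart abstraction for the up to 30 retrospective women, or state that this comparison is limited to prospective women.

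The cost is a few sentences, the choice of a reference, and three extra abstracted fields per retrospective control, some of which the clinic's record may not hold. Prospective women need no new data. The change is therefore cheap but not free: a derivation from Appendix F alone would leave out most of Group 3.

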The BDC is primarily a T1DM clinical and research center and follows large numbers of patients with T1DM. Pregnant women are followed in the Pregnancy and Women's Health clinic at the BDC. All site personnel will attend an investigator's meeting, which will be organized and conducted before trial initiation. All subjects prospectively enrolled will sign an informed consent form approved by the Western Institutional Review Board (WIRB) through the Colorado Multiple Institutional Review Board (COMIRB). A follower, designated by each subject, will also be asked to sign an informed consent form approved by the Western Institutional Review Board (WIRB) through the Colorado Multiple Institutional Review Board (COMIRB), however follower consent will not be obligatory for a pregnant subject to participate in the study. Subjects identified through the retrospective chart review of existing data who are no longer pregnant, may have irregular visits to the Barbara Davis Center and in some cases only return to clinic once per year. As such, these subjects will be contacted by phone or e-mail to see if they are interested in participating in the study. Interested post-partum women will be sent the consent form approved by WIRB through the COMIRB prior to the informed consent discussion. We will undergo consenting procedures with subjects in person, when possible, or by phone and will have subjects sign the consent form and send it back to us. After our staff signs the consent form, subjects will receive a copy of the completed, signed consent form. Communications with the consent form with subjects in the retrospective chart review will take place via e-mail, United States Postal Service, or fax (to be determined by availability, security of devices, and subject preference).

What is the study population?

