There will also be a control arm of pregnant patients at the BDC identified through a retrospective chart review who were pregnant around the time of study enrollment or before and who did not use a CGM device throughout their pregnancies. The retrospective chart review will collect data on a subject's medical history, diabetes complications, medications, vital signs, height/weight, A1C, insulin doses, glucose meter downloads, insulin pump downloads (if applicable), and CGM downloads (if applicable) for the most immediate pre-conception visit, all pregnancy visits, and the post-partum visit. Subjects identified through the retrospective chart review will not have filled out any of our questionnaires (baseline, hypoglycemic fear, and postpartum questionnaires), nor will they have had followers who filled out questionnaires. They will not be asked to fill out these questionnaires.

Inclusion Criteria:

Subjects that meet the following criteria will be considered for admission to the study:

1. Signed informed consent before any study-related activities
2. Female aged 18 years and older with T1D duration >1 year
3. Pregnancy with confirmation of gestational age 13 weeks or less
4. Willingness to routinely practice at least 3-7 blood glucose measurements per day
5. Using MDI or CSII therapy
6. Any A1C level
7. Ability and willingness to adhere to the protocol including scheduled study visits for the duration of the pregnancy
8. Able to speak, read, and write English

Exclusion Criteria:

Subjects will be excluded from the study if any of the following apply:

1. Unwilling to sign informed consent and participate in the study
2. Female age 17 years or younger
3. T1D duration <1 year
4. Pregnancy in gestational week 14 or higher
5. Extensive skin changes/diseases that inhibit wearing a sensor on normal skin
6. Severe known allergy to adhesives within the last 3 months
7. Any other condition, as determined by the investigator, which could make the subject unsuitable for the trial, impairs the subject's suitability for the trial, or impairs the validity of the informed consent

Risks and Justification of Procedures:

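### Most no-CGM controls consent after their pregnancy has ended and have birth outcomes ascertained differently, so the pooled maternal and fetal comparison is open to bias of unknown size and direction

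*Combined protocol and SAP*

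**What the plan says.** **Prospective women.** The third inclusion criterion is "Pregnancy with confirmation of gestational age 13 weeks or less", and women may also be screened before conception. At Visit 14, "Subjects will be administered a questionnaire inquiring about the labor and delivery process, maternal and fetal complications before and after delivery" (the instrument is Appendix F). The same section says that data will be obtained on pregnancies ending in miscarriage, stillbirth or neonatal death.

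**Chart-review women.** Under 'How are we going to do the work?', the plan describes "Subjects identified through the retrospective chart review of existing data who are no longer pregnant" and says that "these subjects will be contacted by phone or e-mail to see if they are interested in participating in the study". It continues: "Interested post-partum women will be sent the consent form". The Control Arm section states: "Subjects identified through the retrospective chart review will not have filled out any of our questionnaires", and then "They will not be asked to fill out these questionnaires". The chart items listed there are history, diabetes complications, medications, vital signs, A1C, insulin doses and device downloads, from the last pre-conception visit to the post-partum visit. No delivery or neonatal outcome is named.

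**Use in the analysis.** 'What are the treatment groups?' places the chart-review women in the no-CGM arm, and 'How many subjects per treatment arm?' allows up to 30 of them. Live birth, pre-eclampsia, birth weight and neonatal hypoglycemia belong to the third secondary outcome. The Statistical Analysis Plan compares outcomes between arms, puts secondary outcomes into the same mixed models, and does not separate the two kinds of control.

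**The concern.** Two distinct problems affect the same comparison.

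The first is entry. A prospective woman joins before anyone knows how her pregnancy will end. A chart-review woman decides whether to join when she already knows, and clinic staff may know too. If willingness or reachability is related to outcome, the live-birth rate among those who consent differs from the rate among all eligible no-CGM pregnancies. The plan does not require consecutive pregnancies, gives no gestational-age rule specific to these women, and does not say whether women with losses are approached.

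The second is ascertainment. Prospective women have a structured questionnaire on delivery, maternal and neonatal events. Chart-review women have whatever a diabetes clinic's chart happens to hold, with no instruction to abstract it. Conditions that must be asked about could be recorded less often in one arm than in the others.

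The Statistical Analysis Plan relies on mixed models to deal with missing data. That cannot help with entry, because a woman who never consents contributes no record. A distorted comparison could also mislead the larger study that 'Weakness of the Study' says this pilot is meant to inform.

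**Working it through.** **Plan's own figures.** Anticipated prospective groups: 10 + 20 + 10 = 40. Completers after 20% drop-out: 40 × (1 − 0.20) = 32. Both reproduce. No live-birth rate, effect size or power is stated, so nothing else can be reproduced.

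**Share of the arm affected.** With 10 prospective and up to 30 chart-review women, the share is 30 / (10 + 30) = 75%. If 20% of the prospective women drop out (8 remain), it is 30 / 38 = 79%.

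**Effect of outcome-dependent entry.** Two inputs are assumptions, not document figures:

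- p: the true live-birth rate, taken as equal in all arms, at 80% or 90%.
- r: the chance that a woman with a loss enters, relative to a woman with a live birth.

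Observed rate among chart-review women = p / (p + (1 − p) × r).

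Rate in the whole no-CGM arm = 0.75 × observed rate + 0.25 × p.

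For p = 0.80 and r = 0.5: 0.80 / (0.80 + 0.20 × 0.5) = 0.889, and the arm rate is 0.75 × 0.889 + 0.25 × 0.80 = 0.867, or +6.7 points.

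| p | r | Chart-review women | Whole no-CGM arm | Spurious difference |
|---|---|---|---|---|
| 0.80 | 1 | 0.800 | 0.800 | 0 |
| 0.80 | 0.5 | 0.889 | 0.867 | +6.7 points |
| 0.80 | 0 | 1.000 | 0.950 | +15.0 points |
| 0.90 | 1 | 0.900 | 0.900 | 0 |
| 0.90 | 0.5 | 0.947 | 0.936 | +3.6 points |
| 0.90 | 0 | 1.000 | 0.975 | +7.5 points |

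**Opposite direction.** If women with losses enter twice as readily (r = 2):

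- p = 0.80: 0.80 / (0.80 + 0.40) = 0.667; arm 0.75 × 0.667 + 0.20 = 0.700, or −10.0 points.
- p = 0.90: 0.90 / (0.90 + 0.20) = 0.818; arm 0.75 × 0.818 + 0.225 = 0.839, or −6.1 points.

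**Sampling error for scale.** The approximate 95% half-width for a difference at equal rates is 1.96 × √(p(1 − p)(1/n₁ + 1/n₂)). This is crude for groups this small.

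- Pooled, 30 CGM against 40 no-CGM women: 19 points at p = 0.80, 14 points at p = 0.90.
- Prospective only, 30 against 10: 29 points at p = 0.80, 21 points at p = 0.90.

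**Ascertainment.** No arithmetic applies. Appendix F asks about complications of pregnancy, labor and the newborn; the Control Arm list contains no matching item. The Control Arm section does cover medical history and the post-partum visit, so some outcomes may be in the chart, but the plan does not say that they will be extracted.

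**The case against.** The strongest reply is that nothing in the plan selects on outcome. Women who are no longer pregnant include those with losses, and post-partum may be loose wording for the same thing. These women have type 1 diabetes and need diabetes care however the pregnancy ended, and phone and e-mail contact reduces dependence on clinic attendance. All of this stands. A reader might infer that the no-CGM arm is enriched for successful pregnancies and the comparison therefore biased against CGM. The documents do not support that: they give no consent rates by outcome, and the direction could be the reverse.

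A second reply is that the two problems partly exclude each other. If birth outcomes are not abstracted, chart-review women cannot distort the live-birth rate; if they are, the complaint about the list falls away. That is fair, and a reader should not treat the missing questionnaire as selection on outcome. But the first case leaves only about 10 controls with structured outcome data, and the second leaves entry after the outcome uncorrected. The plan does not say which applies.

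Third, sampling error exceeds the moderate illustrations. True, but a confidence interval does not reflect this bias, and adding more controls by the same route does not shrink it.

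Fourth, these are secondary outcomes in a pilot with no formal power, retrospective controls are openly declared, and the sentence on secondary outcomes is generic. This limits the weight of the point. Yet the weakness section mentions only non-randomization and pilot status, not post-outcome consent or differing outcome sources.

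**Conclusion.** The point holds as a weakness in the maternal and fetal comparisons with the no-CGM arm. Up to 75% of that arm enters after the outcome and has outcomes ascertained differently, and the plan pools these women without analysis by source.

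The possible distortion in live birth is illustrated, not estimated: +3.6 to +6.7 points if women with losses enter half as often, +7.5 to +15 points if none enter, zero if entry is unrelated to outcome, and negative if women with losses enter more readily. These figures assume equal true rates of 80% to 90% and a 75% chart-review share. The chart-review column in the table should not be read as the effect on the arm, because the prospective quarter dilutes it.

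It should be corrected before the maternal and fetal outcomes are analysed. The point concerns the chart-review part of Group 3, not its prospective women, and it is no evidence that CGM is better or worse than any result would show.

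**What to change.** - **Sampling frame.** Build the chart-review list from all consecutive no-CGM pregnancies at the clinic with a first visit at 13 weeks or less, however they ended, and approach women regardless of outcome.
- **Outcome abstraction.** Name the delivery, maternal and neonatal outcomes to be taken from the chart, with the same definitions as Appendix F, and record when an item cannot be found.
- **Participation.** Report numbers identified, contacted and consented, broken down by pregnancy outcome where ethics approval permits. The breakdown uses data on women who did not consent, so approval should be sought and not assumed.
- **Analysis.** Present live birth and other maternal and fetal outcomes by control source. Show the concurrent prospective comparison separately and label the pooled comparison exploratory.
- **Limitations.** Add post-outcome consent and differing outcome sources to the weakness section.

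The cost is SAP wording, a screening log, extra chart work and possibly an ethics amendment. The prospective-only comparison rests on about 10 controls (about 8 after drop-out) and will have wide intervals. For that reason it should stand beside the chart-review results and not replace them.
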